**Duration of Study:** It is expected that approximately 24 months will be required to complete enrollment in the study. Subjects may discontinue from treatment because of disease progression, unacceptable toxicity, withdrawal of consent, or at the discretion of the Investigator. The last visit for each subject will be defined as the follow up visit which is no less than 90 days after the subject’s end-of-treatment visit. The last visit is either 90 days after last dose or whenever a study drug related toxicity has resolved, stabilized, or been deemed reversible, whichever is latest. The end of the trial will occur on the last visit of the last patient.

**Number of Subjects:** A total of up to 36 subjects are expected to be treated on the study.

**Study Population:** Male and female subjects  $\geq 18$  years of age with a histologic or cytologic diagnosis of unresectable Stage III or Stage IV melanoma and who meet the eligibility criteria (see Sections 3.2.1 and 3.2.2) will participate in the study.

**Investigational Product(s), Dose and Mode of Administration, Duration of Treatment with Investigational Product(s):** Panobinostat is available as 5, 10, 15, and 20 mg capsules and will be administered orally. Ipilimumab is available as sterile dose formulation at 5 mg/mL and will be administered intravenously (IV) as an infusion over 90 minutes. Ipilimumab is not to be administered as an IV push or bolus injection. Panobinostat will be administered at 5, 10 mg, 15 mg, or 20 mg thrice weekly in combination with ipilimumab administered at a dose of 3 mg/kg according to the dose schedule in Table 1. Panobinostat doses beyond 20 mg PO TIW may be considered if appropriate as outlined under study design.

**Study Assessments and Primary Endpoints:** Subjects will be required to visit the investigator’s office or clinic for physical examinations, vital sign measurements, ECOG performance status evaluation, adverse event

assessment, laboratory testing, pharmacodynamic (PD) sample collection, and administration of study drug as per the study schedule.

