- **Safety Outcome Measures:** All subjects who receive study drug therapy will be evaluated for safety. Safety assessments will be based on medical review of adverse event reports and the results of vital sign measurements, physical examinations, and clinical laboratory tests. Triplicate 12-lead electrocardiograms (ECGs) will be collected prior to dosing on Day 1 of induction cycle 1. Single 12-lead ECGs will be collected at screening, prior to dosing on Day 1 of all treatment cycles (with the exception of induction cycle 1 as above) and at the end of treatment.

Adverse events will be categorized using the most current version of MedDRA and adverse events and laboratory tests will be graded using National Cancer Institute (NCI) Common Terminology Criteria for Adverse Events (CTCAE) v4.0. Hepatic adverse events (AST, ALT, T Bili) will also be recorded relative to ULN. Immune-related adverse experiences (irAEs) among treated subjects will be specifically assessed as well.

- **Efficacy Measures:** Tumor response will be determined for all subjects by RECIST 1.1 (see Appendix 3) as well as by immune-related response criteria (irRC; see Appendix 4). RECIST 1.1 will be used for statistical analysis of efficacy in this study. Treatment decisions related to subject management may be based on the irRC criteria, but for the purposes of reporting efficacy RECIST 1.1 criteria will be used. Assessments of tumor status will be made during screening, then at 6 weeks and 12 weeks, and subsequently every 12 weeks. Tumor assessments at the end-of-treatment (EOT) or 90-day follow-up visit will be performed only if not assessed within the prior 12 weeks. Individual subject's best overall response (BOR) will be assessed, and progression free survival (PFS) will be calculated by RECIST 1.1 response criteria. Other endpoints are Objective response (OR) defined as BOR outcome of CR or PR for RECIST 1.1, disease control (DC) defined as BOR outcome of CR, PR, or Stable Disease by RECIST 1.1. Duration of response and duration of disease control will also be calculated.

Statistical Methods:

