# **3 INVESTIGATIONAL PLAN**

## **3.1 Study Design and Duration**

This is a Phase 1 open label study of panobinostat administered in combination with ipilimumab. Subjects with unresectable Stage III or Stage IV melanoma who meet the eligibility criteria will undergo screening evaluations within 28 days prior to initiation of study therapy. The study will consist of a dose escalation assessment of the safety and tolerability of oral panobinostat administered concurrently in combination with ipilimumab. Treatment will be divided into induction with ipilimumab and panobinostat and a maintenance phase with panobinostat alone consistent with the general principles of ipilimumab therapy. It is anticipated that this evaluation will enable selection of the RP2D of this combination for further clinical testing. A study schematic is presented below:

Each treatment cycle will be 42 days (6 weeks) during the induction phase, and 84 days (12 weeks) during the maintenance phase. Panobinostat will be administered orally TIW on Days 1-42 of each 42 day treatment cycle. Ipilimumab will be administered intravenously (IV) once every 3 weeks on Days 1 and 22 of each treatment cycle. The induction phase will last for up to 2 treatment cycles. During the maintenance phase, panobinostat will be administered orally TIW on Days 1-84 of each 84 day treatment cycle. Subjects will continue maintenance panobinostat treatment with their designated combination dose regimen until progression of disease, discontinuation due to toxicity, withdrawal of consent or any other reason as specified in Section 3.4.

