**Table 5.12 During Treatment, Day 1 onward**

Study Cycle	Induction Cycle						Maintenance Cycle	End of Treatment	Follow-up	Notes
Cycle #	1				2		Each Cycle			
Day of Cycle 	1	5	22	35	1	22				
Safety Assessments										
Physical exam	X 		X		X	X	X	X	X	
Ophthalmology Exam	X									Baseline only
Vital Signs	X		X		X	X	X	X	X	
Weight	X		X		X	X	X	X	X	
PS	X 		X		X	X	X	X	X	
ECG	X 	X 			X		X	X		Triplicate 12-lead for Induction Cycle 1 Day 1 & Day 5; single 12-lead ECG otherwise
Chem Panel, CBC	X 		X		X	X	X	X	X	
PT/PTT	X 									
T4, TSH	X 		X		X	X	X			
Serum Preg	X 						X			
Urinalysis	X 				X		X			
SAE Monitoring	X		X		X	X	X	X	X	
Ipilimumab	X		X		X	X				
Panobinostat	X		X		X	X	X 			
Disease Assessment					X		X	X	X	
PD Blood	X		X		X	X	X	X		
Tumor bx				X 						

 All study visits may be scheduled +/- 3 days from planned visit date.

 These tests will not be repeated on Cycle 1 Day 1 of the initial treatment period if completed for screening less than 72 hours (3 days) before the first dose of the study drugs.

 Triplicate ECGs at least 5 minutes apart will be done pre-dose on C1 D1 & C1 D5.

 Biopsy to be done between Days 35 and 42.

 Panobinostat will continue to be administered thrice weekly during the maintenance cycles.

6. Patients will continue to be followed for PFS and OS.

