### 8.2.2 Efficacy Endpoints

#### 8.2.2.1 Efficacy Endpoints based on RECIST 1.1

The best overall response (BOR), computed for all treated subjects, is defined as the best response designation over the study as a whole, recorded between the dates of first dose until the last tumor assessment prior to subsequent therapy.

**Objective Response Rate (ORR)** is defined as the total number of subjects whose best response outcome is a complete response (CR) or partial response (PR) divided by the total number of evaluable subjects.

**Disease Control Rate (DCR)** is defined as the total number of subjects whose best response outcome is a complete response (CR) or partial response (PR), or stable disease divided by the total number of evaluable subjects.

**Prolonged Disease Control Rate (PDCR)** is defined as the total number of subjects whose best response outcome is a complete response (CR) or partial response (PR), or stable disease lasting at least 12 weeks, divided by the total number of evaluable subjects.

**Progression Free Survival (PFS):** is defined for each subject as the time from first dosing to the first observation of disease progression or death due to any cause. If a subject has not progressed or died at the time of analysis, PFS will be censored on the date of the last disease assessment. Subjects who do not have any tumor assessment on treatment will be censored on the day of the first dose.

**Duration of Overall Response:** will be computed for all subjects whose best response is either a PR or CR and is calculated from the time the measurement criteria are met for PR or CR, whichever is recorded first, until the date of documented progressive disease or death.

**Duration of Disease Control:** will be computed for the subjects who had BOR outcome of CR, PR, or Stable Disease and is calculated from the beginning of treatment until the time of documented disease progression.

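### The first-dose censoring sentence for PFS and irPFS conflicts with the endpoint definitions and, read literally, discards progression or death in subjects who stop before the week 6 scan

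*Combined protocol and SAP*

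**What the plan says.** Section 8.2.2.1 defines PFS as time from first dose to the first observed progression or death from any cause, with no on-treatment limit. It then censors at the last disease assessment, but only for subjects who have neither progressed nor died. The closing sentence drops that condition: "Subjects who do not have any tumor assessment on treatment will be censored on the day of the first dose". 

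Section 8.2.2.2 repeats the sentence for irPFS. The same paragraph already has a separate rule that censors at first dose when no post-baseline assessment is recorded, and another that makes death without irPD an event.

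On scan timing, the Synopsis (Efficacy Measures) says: "Assessments of tumor status will be made during screening, then at 6 weeks and 12 weeks, and subsequently every 12 weeks". It adds: "Tumor assessments at the end-of-treatment (EOT) or 90-day follow-up visit will be performed only if not assessed within the prior 12 weeks". Table 5.12 marks disease assessment at end of treatment and at follow-up with no such condition, and its footnote 6 says: "Patients will continue to be followed for PFS and OS". Neither Section 8 nor the schedule says whether an EOT scan taken after the last dose counts as on treatment.

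**The concern.** A subject who stops study drug before the week 6 scan may have a first post-baseline scan only at the 90-day follow-up visit. The closing sentence, taken at its word, then assigns Day 0 censoring whatever that scan shows, and also if the subject has died. A time censored at Day 0 leaves the Kaplan-Meier risk set before the first event, and it contributes S(0) = 1 to the parametric fit that Section 8.3.2 also plans. In effect the subject is deleted from both analyses.

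These subjects are not a random subset. Section 4.3.6 takes subjects with a hepatic DLT or a Grade 3 or worse irAE off study, and Table 4.2 can discontinue a subject for QTcF as early as Cycle 1 Day 5. Section 3.1 replaces subjects who miss the DLT period for reasons other than drug toxicity, but not those who stop for toxicity, so the latter remain part of a small MTD group. Two analysts following the same text could report different PFS results from the same data.

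**Working it through.** The plan gives no PFS sample size, event count or power, so there is no figure of its own to reproduce. The check is day arithmetic, a comparison of the rules, and an illustration on stated assumptions.

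**Inputs.** Screening: subjects "will undergo screening evaluations within 28 days prior to initiation of study therapy" (Section 3.1); Appendix 3 tolerates a baseline of about 30 days. Visit window: "All study visits may be scheduled +/- 3 days from planned visit date" (Table 5.12). Scan exemption: 12 weeks = 84 days (Synopsis). Last visit: a "follow up visit which is no less than 90 days after" the EOT visit (Synopsis, Duration of Study). First dose is Day 1, and the week 6 scan falls on Cycle 2 Day 1 (Day 43).

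**Step 1: is an EOT scan due under the Synopsis?** Oldest possible screening scan at the stop = days before first dose + (stop day − 1).
- Scan on Day −28, stop on Day 42: 28 + 41 = 69 days.
- Scan on Day −28, stop on Day 45 (week 6 scan three days late): 28 + 44 = 72 days.
- Scan 30 days before dosing, stop on Day 45: 30 + 44 = 74 days.

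All are below 84, so no EOT scan is due if the EOT visit follows within 84 − 74 = 10 days of stopping. There is an edge case: Section 4.3.6 allows cycle delays of up to 14 days after a DLT, and Section 5.3 delays scans to match. Then 28 + 42 + 14 = 84 days, or 87 with the visit window, and the scan could become due.

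**Step 2: is the 90-day scan due?** Shortest gap, with the scan on Day −1 and the stop on Day 1: 1 + 90 = 91 days, above 84. The scan is due, and it is off treatment.

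**Step 3: what happens to a progression seen at that scan, or to a death?**
- PFS definition: an event.
- General censoring sentence: does not apply, because the subject has had an event.
- Closing sentence, read literally: censored at first dose.
- irPFS: the death rule makes a death an event, while the closing sentence, and the no-post-baseline rule if there was no scan, censor it at first dose.

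**Step 4: how many subjects?** Table 8.1 declares the MTD with 3 DLTs among 12 subjects. If all three led to removal before week 6, 3/12 = 25% of the group would be affected. The documents give no early-stopping rate. For an assumed rate q, the chance of at least one early stopper among 12 is 1 − (1 − q)^12: 46% for q = 5%, 68% for 9%, 91% for 18%.

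**Step 5: effect on PFS.** Assume 12 subjects at the MTD, 5 event-free at week 24, no other censoring, and k early stoppers who all progress by week 24. Week-24 PFS is 5/12 = 41.7% if those progressions count. Censored at Day 0 it is 5/(12 − k): 5/11 = 45.5%, 5/10 = 50.0%, 5/9 = 55.6% for k = 1, 2, 3. The rise follows from assuming that every dropped subject progressed.

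The median is less predictable, because progression first seen at the 90-day scan is dated late. In a rough simulation (exponential PFS, n = 12, early stoppers scanned at about week 17), Day 0 censoring moved the Kaplan-Meier median both ways. With a true median of 12 weeks for everyone and k = 2, it came out later in 9% of runs and earlier in 32%. With 24 weeks for those continuing, 12 weeks for early stoppers and k = 3, it came out later in 39% and earlier in 8%.

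**The case against.** The strongest reply is that the closing sentence follows directly on a sentence about subjects without an event, and may only supply their censoring date when there are no scans. On that reading the PFS definition governs and nothing is lost. This is a fair reading, possibly the intended one, and it stands to this extent: the defect is a conflict between sentences, not a settled instruction to ignore documented progression. It does not remove the problem. In Section 8.2.2.2 a rule for subjects with no post-baseline scan already exists, so the closing sentence is either redundant or reaches subjects who do have such a scan.

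A reader might go further than the documents allow:
- *That all off-treatment progression is ignored.* Even the literal sentence touches only subjects with no on-treatment scan. Appendix 4 (Section 4.4) permits extra scans on suspicion of progression, and one taken before stopping avoids the problem.
- *That the EOT scan is never done.* Only the Synopsis waives it; Table 5.12 lists it, and dosing delays or a late EOT visit can make it due.
- *That a quarter of the MTD group is lost.* The DLT window is 84 days, and half of it follows week 6. Section 4.3.6 also lets some first DLTs restart treatment.
- *That PFS would describe only those who tolerated treatment, or that its median is inflated.* Toxicity stoppers with an on-treatment scan stay in the analysis, and Step 5 gives no fixed direction for the median.

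**Conclusion.** The concern holds as a conflict that should be resolved before analysis. Followed literally, the closing sentence contradicts the PFS definition, the irPFS death rule and the continued PFS follow-up in Table 5.12. The Synopsis exemption makes the situation more likely for anyone stopping before week 6. This rests on the screening scan counting as an assessment, a prompt EOT visit, no long dosing delay and no unscheduled on-treatment scan.

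The number affected is small: 3 of 12 is an upper illustration, and the documents give no rate from which to expect a particular figure. In so small a group even one or two subjects can shift a reported PFS proportion by several points, as in the assumed example, but no direction of bias in the median should be asserted. PFS is a descriptive secondary measure with no planned test, and MTD selection does not depend on it.

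**What to change.** 1. In Section 8.2.2.1, limit first-dose censoring to subjects with no post-baseline tumor assessment who have not died. State that progression or death, on or off treatment, is an event on its date, and add a rule for subsequent anti-cancer therapy. Changing *on treatment* to *post-baseline* alone is not enough, because a death before any scan would still be censored at Day 0.
2. In Section 8.2.2.2, delete the repeated on-treatment sentence and make the existing no-post-baseline rule subject to the death rule.
3. Reconcile the Synopsis with Table 5.12 on whether the EOT disease assessment is done when no post-baseline scan exists.

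The cost is a few sentences in the Synopsis and Section 8. If the sponsor keeps the EOT assessment for these subjects, Table 5.12 already lists it.

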**8.2.2.2 Efficacy Endpoints based on Immune Related Criteria (irCR)**

**Immune Related Best Overall Response (irBOR)** is the best irRC designation over the study as a whole, recorded between the date of first dose until the last tumor assessment prior to subsequent therapy (except for local palliative radiotherapy for painful bone lesions) for the individual subject in the study. irCR or irPR determinations included in the irBOR assessment must be confirmed by a second (confirmatory) evaluation meeting the criteria for response and performed no less than 4 weeks after the criteria for response are first met.

**Immune-related Response Rate (irRR)** is defined as the proportion of response evaluable subjects whose irBOR outcome is irPR, irCR.

**Immune-related Disease Control Rate (irDCR)** is defined as the proportion of the response evaluable subjects whose irBOR outcome is irPR, irCR, or irSD.

**Immune-related Prolonged Disease Control Rate (irPDCR)** is defined as the proportion of the response evaluable subjects whose irBOR outcome is irPR, irCR, or irSD, with stable disease lasting at least 12 weeks.

**Immune-related Progression-Free Survival (irPFS)** is defined as the time between the first dosing date and the date of irPD or death, whichever occurs first. For subjects with no recorded post-baseline tumor assessment, irPFS will be censored at the day of first dose. A subject who dies without reported irPD will be considered to have progressed on the date of death. For those who remain alive and have no irPD, irPFS will be censored on the date of last evaluable tumor assessment. Subjects who do not have any tumor assessment on treatment will be censored on the day of the first dose.

**Duration of Immune Related Overall Response:** will be computed for all subjects whose irBOR outcome is either an irPR or irCR and is calculated from the time the measurement criteria are met for irPR or irCR, whichever is recorded first, until the date of documented progressive disease or death by irRC.

**Duration of Immune Related Disease Control:** will be computed for the subjects who had irBOR outcome of irCR, irPR, or ir Stable Disease and is calculated from the beginning of treatment until the time of documented disease progression by irRC.

## 8.3 Analyses

### 8.3.1 Demographics and Baseline Characteristics

Frequency distributions of gender and race will be tabulated by dose. Summary statistics for age, body weight, height, and Body Mass Index (BMI) will be tabulated by dose.

### 8.3.2 Efficacy Analyses

Listings of tumor measurements will be provided by subject and study day in each arm. Individual subject's best overall response (BOR) and progression free survival (PFS) will be listed based on RECIST 1.1 (dose escalation and cohort expansion). To describe the anti-tumor activity of panobinostat administered in combination with ipilimumab, Objective Response Rate (ORR) as well as prolonged disease control rate by RECIST 1.1 (PDCR) will be similarly summarized. Objective Response (OR) is defined as BOR outcome of CR or PR by RECIST 1.1. Disease Control (DC) defined as BOR outcome of CR, PR, or Stable Disease by RECIST 1.1. Prolonged disease control is defined as disease control with stable disease of at least 12 months. Duration of response and duration of disease control will also be calculated for the subjects with such outcome, based on both efficacy criteria. Median PFS, Duration of Response, and Duration of Disease Control will be estimated by Kaplan-Meier method and with 95% confidence intervals, at the MTD based on both response criteria. Kaplan Meier plots will be provided for all time-to-event variables at the MTD, based on both response criteria. We will also fit the survival function using a parametric survival approach, as this approach provides a more accurate estimate of the median PFS. Additional assessments, e.g. sensitivity analyses may be performed to characterize clinical activity. The relationship between panobinostat exposure/dose and clinical efficacy (e.g. tumor response based on RECIST 1.1 criteria) may be explored graphically and appropriate model may be fit.

### 8.3.3 Safety Analyses

All recorded adverse events will be listed and tabulated by system organ class, preferred term, and dose and coded according to the most current version of MedDRA. The incidence of adverse events will be tabulated and reviewed for potential significance and clinical importance. Vital signs and clinical laboratory test results will be listed and summarized by and dose. Any significant physical examination findings and results of clinical laboratory tests will be listed. ECG listings will be evaluated by the investigator and abnormalities, if present, will be listed. A separate listing and summary of all immune-related adverse events (irAE) and inflammatory events regardless of causality (IERC) will be provided. In addition, the irAE rate will be estimated and a 90% confidence interval will be constructed for the irAE and the grade 3-4 GI irAE rate in each arm, based on the Clopper-Pearson method. The relationship between panobinostat exposure/dose and adverse event may be explored graphically and appropriate model may be fit.

### 8.3.4 Biomarker Analyses

Pharmacodynamic analyses will examine the patterns of change in ALC over time, and how these patterns might differ between treatment arms. Predictive analyses will examine potential relationships between ALC and measures of response such as PFS or irPFS. The mean rate of change in ALC over time and corresponding two-sided 95% CIs will be estimated using an extended linear model, fit by restricted maximum likelihood (REML). The model will have fixed effects of treatment and time since first dose. Predictive analyses will assess the relationship between PFS / irPFS and rate of change in ALC over time (ALC slope). Summary statistics for peripheral blood biomarkers of immunoregulatory activity such as, but not limited to T-cell subpopulation counts, serum cytokines, and their corresponding changes (or percent changes) from baseline will be tabulated by planned study day and dose in each arm, to assess pharmacodynamic effects. In addition, the time course of biomarker measures will be investigated graphically; if there is indication of meaningful pattern across time, further analysis (eg, by linear mixed models) may be performed to characterize the relationship. Possible associations between changes in biomarker measures of interest and panobinostat exposure will be explored graphically. Summary statistics for measures and changes from baseline of tumor-based markers including T-cell (CD4, CD8, CD45, FoxP3) and apoptosis markers (IDO and granzyme B) will be tabulated by study visit for each arm. Results from mRNA expression profiles pre- and on-treatment, in peripheral blood and fresh tumor biopsies and from T cell phenotype analysis on baseline samples will be tabulated, and possible associations with clinical outcome (e.g. tumor response) will be explored based on data availability. Associations between biomarkers and efficacy measures will be analyzed in all response-evaluable subjects. Methods such as, but not limited to, logistic regression will be used to explore possible associations between biomarker measures from peripheral blood or tumor markers and clinical outcome, e.g. tumor response, based on both RECIST 1.1 and irRC criteria.

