#### **1.4.6 Rationale for use of Blood and Tumor Tissue Biomarkers**

Previous ipilimumab studies explored in their main study design a variety of potential biomarkers in melanoma patients. Results from studies CA184004 and CA184007 suggested the possible biomarkers listed below for further research:

- An increase in peripheral-blood Absolute Lymphocyte Count (ALC) was associated with benefit (Best Overall Response of Complete Response, Partial Response, or prolonged Stable Disease (SD), i.e. SD lasting at least 24 weeks from first dose) and occurred in a dose-dependent fashion favoring 10 mg/kg ipilimumab. In addition to change in ALC over time, ALC value just prior to a third dose of ipilimumab also was associated with benefit.

We will also evaluate FOXP3 and IDO tumor tissue expression at baseline as predictive of clinical benefit, as well as flow cytometry of CD4 and CD8 T cells for Ki67, EOMES and ICOS, predictive markers that have been found to be associated with benefit using ipilimumab. Serum cytokine assays with a multiplex analysis for IL-6, IL-10 and gamma interferon will be conducted, as well as T cell intracellular staining for those cytokines and assessment of allo MLR reactivity as a marker of T cell integrity.

[figure not shown]
A mean increase in the percentage of activated (HLA-DR+), CD4+ and CD8+ T cells and central memory (CD45-RO and CCR9+) T-cells and a mean decrease in percent of naive CD4+ and CD8+ T-cells in Week 4 and Week 12 post-ipilimumab treatment samples has been observed in several studies. Based on these results, a biomarker plan is included in this trial which allows sample collection for biomarker analyses to determine the effects of PANOBINOSTAT on the immune-regulatory effects of ipilimumab treatment. Subjects will

be asked to give blood samples, serum and/or tumor tissue samples for predictive, pharmacodynamic and exploratory biomarker research.

[figure not shown]

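### The single ALC slope in Section 8.3.4 has no visible window or change of slope at the end of induction, so it can mix two treatment phases and depend on length of follow-up

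*Combined protocol and SAP*

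**What the plan says.** Section 8.3.4 sets a broad aim for ALC: "Pharmacodynamic analyses will examine the patterns of change in ALC over time, and how these patterns might differ between treatment arms". It then names the estimate: "The mean rate of change in ALC over time and corresponding two-sided 95% CIs will be estimated using an extended linear model", fitted by REML. On the form of the model it says only: "The model will have fixed effects of treatment and time since first dose". The same slope is carried into analyses of PFS and irPFS.

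Section 3.1 describes a planned change of treatment. "Ipilimumab will be administered intravenously (IV) once every 3 weeks on Days 1 and 22 of each treatment cycle", for up to two 42-day cycles, which puts the doses at weeks 0, 3, 6 and 9. After that comes "a maintenance phase with panobinostat alone", in 84-day cycles. Table 5.12 schedules the CBC at the four induction dosing visits, in each maintenance cycle, at end of treatment and at follow-up. Section 5.3.1 includes the differential, so ALC will be available after ipilimumab has stopped.

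The rationale in Section 1.4.6 comes from ipilimumab studies. It cites a dose-dependent ALC increase associated with benefit, and adds that "ALC value just prior to a third dose of ipilimumab also was associated with benefit". In this schedule the third dose falls at week 6. The documents give no ALC course after week 12.

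**The concern.** A rate of change estimated from one time term assumes that ALC moves at the same rate while ipilimumab is being given and after it has stopped. The design gives reason to doubt this, because the drug that motivates the ALC marker is withdrawn while measurement goes on. Maintenance visits are also 12 weeks apart, so they lie far from the mean time and weigh heavily in a least-squares slope.

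At stake is the pharmacodynamic part of the secondary objectives, together with the predictive analysis that uses the slope. If the rate changes after induction, the slope describes neither phase, and two groups with the same early ALC response could show different slopes only because one was followed longer.

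**Working it through.** The plan states no expected ALC slope, variance or trajectory, so there is no figure to reproduce. The check asks how far one fitted line departs from the induction slope under assumed later courses.

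**Inputs.** Visit weeks 0, 3, 6, 9, 12, then every 12 weeks (Section 3.1, Table 5.12). *Assumption:* mean ALC rises by 1 unit per week to week 12, then changes by p units per week.

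**Formula.** The fitted slope is b = Σ(t − t̄)(y − ȳ) / Σ(t − t̄)². It is linear in p, so b(p) = b₀ + p(1 − b₀), where b₀ is the value under a plateau (p = 0).

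**Plateau, every subject attending every visit.**
- Last visit week 24: 180 / 360 = 0.50
- Week 36: 295.7 / 984.9 = 0.30
- Week 48: 427.5 / 2065.5 = 0.21
- Week 72: 720 / 5940 = 0.12

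**Other later courses, from b(p), full retention.**

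| Course after week 12 | wk 24 | wk 36 | wk 48 | wk 72 |
|---|---|---|---|---|
| Same rise (p = 1) | 1.00 | 1.00 | 1.00 | 1.00 |
| Half-rate rise (p = 0.5) | 0.75 | 0.65 | 0.60 | 0.56 |
| Plateau (p = 0) | 0.50 | 0.30 | 0.21 | 0.12 |
| Half-rate fall (p = −0.5) | 0.25 | −0.05 | −0.19 | −0.32 |

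The slope becomes negative only if p is below −b₀/(1 − b₀), which is −1.00, −0.43, −0.26 and −0.14 for these last visits.

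**Allowing for dropout.** Section 1.4.2.3 reports about 11% progression-free at 6 months and 6% at 1 year for ipilimumab 3 mg/kg (N = 37). I took these as retention at weeks 26 and 52, with a constant hazard between: S(t) = 0.11^(t/26) to week 26, then 0.11 × (0.06/0.11)^((t − 26)/26), extrapolated beyond week 52. Visit weights are 1, 0.775, 0.601, 0.466, 0.361 through week 12, then 0.130, 0.087, 0.066, 0.050 and 0.038 at weeks 24 to 72.
- For last visit week 24, the weighted sums are about 71.3 / 100.5 = 0.71.
- The plateau ratios are 0.71, 0.50, 0.37 and 0.24. Other early shapes through the same two points (straight-line loss, or no loss until week 6 or week 12) give 0.70–0.77, 0.50–0.57, 0.37–0.42 and 0.24–0.27.
- Under a half-rate fall the slope stays positive through week 48 (0.06 to 0.13 there) and is negative only by week 72 (−0.13 to −0.10).

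**Mixed-model check.** A REML random-intercept simulation used 36 subjects, assumed variances, and dropout lighter than the figures above (last visit at week 6, 12, 24, 36 or 60 for 15%, 40%, 20%, 15% and 10%). With all visits it gave 1.00 of the induction slope if the rise continued, 0.29 under a plateau and −0.05 under a half-rate fall. Restricted to visits through week 12 it gave 0.98 to 1.01 in every scenario.

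**If the turn comes at the last dose (week 9).** With full retention a plateau gives 0.35, 0.20 and 0.13 for last visits at weeks 24, 36 and 48. Visits through week 12 alone then give 0.80, so a week-12 boundary removes most of the attenuation, not all of it.

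**The case against.** A reader might infer that the plan fits a straight line from first dose through maintenance and that the slope is therefore flattened or reversed. The documents do not support that as fact, for three reasons.

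- **The visit range is not stated.** The inclusion of maintenance values is inferred because Section 8.3.4 shows no window. The table of contents lists a Section 5.5.1 on ALC whose text is redacted, and a window could be set there.
- **The later ALC course is unknown.** Panobinostat continues in maintenance. A rise at the same rate would leave the slope undistorted.
- **The larger effects assume full retention.** With retention near the protocol's own figures the attenuation is smaller, and sign reversal is late or absent.

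Section 8.3.4 also tabulates blood biomarkers by planned study day, plots their time courses, and adds that "if there is indication of meaningful pattern across time, further analysis (eg, by linear mixed models) may be performed to characterize the relationship". The tables and plots would probably reveal a change at the end of induction. The objective concerns the whole regimen, including maintenance, so an induction slope is not the only defensible target.

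All of this limits the size and certainty of the point. It does not remove it. Further modelling is optional and is worded for biomarkers in general. It does not alter the named ALC slope or its use against PFS. A reader interested in the whole regimen is also better served by two slopes than by an average whose weights depend on who stays on treatment.

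**Conclusion.** The point holds conditionally and is a modest improvement to a secondary analysis. As visible, Section 8.3.4 yields one ALC slope across a planned change of treatment. Unless the redacted Section 5.5.1 restricts the window, and unless ALC keeps changing at the induction rate, that slope mixes two phases and depends on follow-up.

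Under an assumed plateau after week 12 it is 0.50 to 0.12 of the induction slope for last visits at weeks 24 to 72 with full retention, or about 0.7 to 0.25 with retention near the 3 mg/kg progression-free figures. A half-rate later rise gives 0.75 to 0.56 with full retention. These sizes rest on an assumed piecewise-linear course and on progression-free status standing in for retention. CBCs at end of treatment and follow-up could add later values that the retention weights leave out.

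The primary objective, dose escalation and sample size are untouched.

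**What to change.** In Section 8.3.4, add to the ALC model a change of slope at the end of induction (week 12), for example a term equal to time beyond week 12 and zero before it. Report the induction slope and the maintenance slope, each with a two-sided 95% CI. Name the induction slope as the main pharmacodynamic estimate, and leave the other model terms as stated. If Section 5.5.1 already sets a window, repeat it in Section 8.3.4.

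The cost is one extra model term and slightly wider intervals. The maintenance slope will be imprecise if few subjects reach maintenance, and its interval will show that. No visit, sample or sample size changes.
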